#### 2.1.2 Exploratory Objectives

- To explore the preliminary efficacy of PA-SEGT for improving demoralization, complicated grief, depression, PTSD, shame, anxiety, post-traumatic growth, quality of life, functional social support, openness to experience, attachment security, social connection, nature relatedness and ART medication adherence in LTAS.
- To explore quantitatively and qualitatively the mechanisms (e.g. group cohesion) through which PA-SEGT addresses demoralization and other mental health outcomes in LTAS.

### 2.2 Endpoints

#### 2.2.1 Primary Endpoints

- Safety will be defined based on the rate of adverse reactions (defined by the NIH Division of AIDS Table of Grading of Severity of Adult and Pediatric Adverse Events V2.0) (see Section 5 below). The safety of acute drug effects will be assessed by monitoring vital signs for tachycardia (HR>100bpm), bradycardia (HR<60bpm), hypertension (SBP>140mmHg or DBP>90mmHg) and hypotension (SBP<100mmHg or DBP<60mmHg). Drug-induced mental status changes will be assessed using the Adverse Event Medication Session Rating Form during drug sessions, pre and post measures with the Montreal Cognitive Assessment, and the Persisting Effects Questionnaire—Spirituality at study follow up. Suicidality will be assessed with the Columbia Suicide Severity Rating Scale. Follow-up safety data will be gathered for 3 months.
- Feasibility will partially be assessed in terms of the rates of patient recruitment and retention. Feedback on acceptability will also be gathered from subjects and caregivers/important others using the Client Satisfaction Scale. Patients and caregivers will also be invited to provide feedback during a focus group and patients will be invited to participate in individual interviews after the intervention. A SEGT Topic Grid will be used to evaluate video recordings of group therapy sessions in order to assess therapist adherence to the PA-SEGT model.

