Safety Assessments	Adverse events Vital signs  Adverse Event Medication Session Form  Columbia Suicide Severity Rating Scale  Community Observer Rating Form
Feasibility Assessments	Rate of Patient Recruitment Rate of Patient Retention (Sessions Attended and Follow-ups Completed) Client Satisfaction Scale Individual Patient and Important Other/Caregiver Interviews Supportive-Expressive Group Therapy Topic Grid Focus Groups with Patients and Important Others/Caregivers
Primary Outcomes	Demoralization Scale-II Inventory of Complicated Grief
Secondary Outcomes	Antiretroviral Medication Adherence Scale Alcohol Use Disorders Identification Test Center for Epidemiologic Studies Depression Scale—Revised Challenging Experience Questionnaire Clinical Global Impressions Scale Credibility/Expectancy Questionnaire Duke/UNC Functional Social Support Questionnaire—5 Drug Use Disorders Identification Test Experiences in Close Relationships scale—Modified 16 Group Psychotherapy Intervention Rating Scale Group Questionnaire HIV and Abuse Related Shame Inventory Individual Group Member Interpersonal Process Scale International Personality Item Pool—Openness to Experience-20 McGill Quality of Life Questionnaire—Revised-Short Multidimensional Assessment of Interoceptive Awareness—Revised Mystical Experience Questionnaire—30 Nature Relatedness Scale, Short Form Post-traumatic Growth Inventory—Short Form PTSD Checklist-5 Schedule of Attitudes towards Hastened Death Social Connectedness Scale-Revised

	State-Trait Anxiety Inventory Qualitative analysis of therapy sessions, interviews & focus groups
--	--

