- Change in mindfulness will be defined as the difference in pre-treatment, post-treatment, and 3-month follow-up mean scores of subscales of the Multidimensional Assessment of Interoceptive Awareness.
- Change in social connectedness will be defined by the difference in pre-treatment, post-treatment, and 3-month follow-up mean scores of the Social Connectedness Scale—Revised.
- Change in Nature Relatedness will be defined by the difference in pre-treatment, post-treatment, and 3-month follow-up mean scores of the Nature Relatedness Scale, Short Form Version.
- Change in alcohol and drug use will be defined by different in the baseline and 3-month follow-up AUDIT and DUDIT scores

Psychotherapeutic process and mechanisms will be explored with the following endpoints:

- Change in group cohesion will be defined as the difference in rate of Group Questionnaire score change pre- and post-psylocybin.
- Change in group process will be assessed as the difference in rate of progression of

---

the Hill Interaction Matrix score pre- and post-psilocybin.

- Change in group process will be assessed as the change in the Individual Group Member Interpersonal Process Scale over time.
- Expectancy effects will be estimated based on the pre-psilocybin total score of the Credibility/Expectancy Questionnaire.
- Subjective experience of a psilocybin treatment session will be evaluated with the Mystical Experience Questionnaire—30 and the Challenging Experience Questionnaire.
- Change in attachment security will be defined as the difference in pre-treatment, post-treatment, and 3-month follow-up mean scores of the Experiences in Close Relationships scale—Modified 16.
- Qualitative analysis of therapy session video footage, semi-structured patient interviews, focus groups and process notes written by study staff.
- Change in inclusion of other in self will be defined by the difference in pre-treatment, post-treatment, and 3-month follow-up results of the Inclusion of Other in Self measure.

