Palliative Performance Scale version 2 (PPSv2)—A validated clinician-administered tool based on the Karnofsky Performance Scale but adapted for a palliative care population [113, 171].

Persisting Effects Questionnaire—Spirituality (PEQ-S)—An instrument developed by Griffiths et al for subjects who have been administered psilocybin to assess enduring changes in attitudes about life, attitudes about self, mood changes, relationships, behavioral changes, and spirituality [138]. The measure also includes 4 questions about the drug experience itself concerning personal meaningfulness, spiritual significance, how psychologically challenging it was, and personal psychological insights gained. We will only use the Spirituality subscale (59-item, 6 point Likert scale [“none; not at all” to “extreme”]), and the four questions about the psilocybin experience.

Post-traumatic Growth Inventory-Short Form (PTGI-SF)—A validated 10-item 6-point Likert scale meant to assess the following psychological factors in populations that have suffered a traumatic event or major crisis: quality of relationships with others, openness to new possibilities, personal strengths, spiritual change, and appreciation of life [172].

PTSD Checklist (PCL-5): A validated 20-item, 5-point Likert scale (from “Not at All” to “Extremely”) to measure symptom criteria for PTSD from the DSM-5. [Weathers, F.W., Litz, B.T., Keane, T.M., Palmieri, P.A., Marx, B.P., & Schnurr, P.P. (2013). The PTSD Checklist for DSM-5 (PCL-5)]

Quality of Life in Life Threatening Illness Family Caregiver version 2 (QoLLTI-Fv2)—A validated 17-item 11-point Likert scale (0-10) self-report measure that assesses seven domains of quality of life in caregivers for patients with life-threatening illness: state of carer, patient well-being, quality of care, outlook, environment, finances and relationships. This instrument was developed by the same laboratory that developed the McGill Quality of Life scale [173].

Schedule of Attitudes towards Hastened Death (SAHD)—A 20-item True/False self-report measure of the desire for hastened death validated in patients with HIV/AIDS and other palliative care conditions [174].

Social Connectedness Scale-Revised (SCS-R)—A well-validated 8-item 6-point Likert scale (negatively-worded items rated from “strongly agree” to “strongly disagree”) self-report measure which has shown strong construct, convergent and discriminant validity as well as reliability ( $\alpha >$

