## 6.4.3 Baseline Assessments (Week 1)

### 6.4.3.1 Baseline Subject Assessments

Baseline assessments will be filled out during an individual therapy session wherein the subject will meet one or both of the group therapists in the week prior to the first group therapy session. Separately, the subject's caregiver/important other will be invited to meet with study staff for a brief interview on their relationship with the subject [see Appendix C for interview guides]. The individual session for the study subject is meant to build trust and rapport with the group therapists, to learn more about the subject's life history and struggles with his health, to elicit the subject's preferences and intentions for the treatment sessions, and to orient the subject further to the intervention protocol. If screening/enrollment measures were completed within 1 week of the baseline assessment, those measures will not need to be repeated.

- AMAS, AUDIT, CESD-R, CTC, DS-II, DUDIT, DUFSS-5, ECR-M16, ICG, IOS, IPIP-OE-20, MAIA-R, MQoL- RS, NR-6, PCL-5, PTGI-SF, SAHD, SCS-R, and STAI. A clinical rater will perform a CGI and C-SSRS(Interval) for each subject.

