## **6.4.5 Endpoint Assessments**

### **6.4.5.1 Endpoint (Week 8) Study Measures for Subjects**

Immediately after the last group therapy session (Week 8), patients will complete the AMAS, CESD-R, DS-II, DUFSS-5, ECR-M16, ICG, IOS, MQoL-RS, NR-6, PCL-5 SAHD, SCS-R, STAI, PTGI-SF, IPIP-OE-20, MAIA-R, HARSI, CTC, and CSS. A clinical rater will perform a MoCA and CGI for each subject.

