## 7 Reporting and Documentation of Results

### 7.1 Evaluation of Safety and Feasibility

The assessment of safety and feasibility will be informed by surveillance of adverse events in all patients who enroll in the study. The study will use the NIH Division of AIDS Table of Grading of Severity of Adult and Pediatric Adverse Events V2.0 for reporting of adverse events. Analyses of feasibility and acceptability will also be informed by rates of patient recruitment and retention, therapist protocol adherence, self-report measures (CrEQ and CSS), and spontaneous feedback from subjects, caregivers/important others, and study therapists.

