## 8.5 Primary Analysis

Safety analyses will be performed for all patients who enroll in the study. The study will use the NIH Division of AIDS Table of Grading of Severity of Adult and Pediatric Adverse Events V2.0 to

classify adverse events. Descriptive statistics (percentages) will be reported for the incidence of any Adverse Events reported, including suicidality as measured by the C-SSRS. Median scores will also be calculated for total scores of the feasibility measures: CSS, CrEQ, and PEQ-S. The differences of mean pre- and post-treatment scores on the CORF will be calculated. Differences in individual pre- and post-treatment MoCA scores will be assessed for each individual. Therapist protocol adherence will be reported as a rate of discussion topic deviations from the protocol.

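### PEQ-S is named in the primary safety endpoint and the primary analysis but is on no visit list, and IOS lacks the 3-month collection its endpoint requires

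*Combined protocol and SAP*

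**What the plan says.** **PEQ-S.** Section 2.2.1 names three tools for drug-induced mental status changes: the medication-session adverse event form, the MoCA before and after treatment, and "the Persisting Effects Questionnaire—Spirituality at study follow up". Section 8.5 then states: "Median scores will also be calculated for total scores of the feasibility measures: CSS, CrEQ, and PEQ-S". Section 6.2 describes the instrument as a 59-item Spirituality subscale plus four questions on the drug experience, without naming a visit. Section 7.1 gives the self-report feasibility measures as CrEQ and CSS only. The Abstract lists PEQ-S under neither safety nor feasibility.

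**IOS.** Section 2.2.2 defines the endpoint by the difference in pre-treatment, post-treatment and "3-month follow-up results of the Inclusion of Other in Self measure". The baseline list in Section 6.4.3.1 includes it ("AMAS, AUDIT, CESD-R, CTC, DS-II, DUDIT, DUFSS-5, ECR-M16, ICG, IOS, IPIP-OE-20, MAIA-R"), and so does the Week 8 list in Section 6.4.5.1 ("AMAS, CESD-R, DS-II, DUFSS-5, ECR-M16, ICG, IOS, MQoL-RS, NR-6"). The 3-month packet in Section 6.4.6.2 does not, and Section 6.2 has no description of IOS.

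**HARSI.** Section 1.4 hypothesises a pre-to-post improvement in shame. In the Section 6.4 text, HARSI is collected at session 5, Week 8 and 3 months.

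**The concern.** Sites collect what the visit lists tell them to collect. A measure that appears in an endpoint definition or an analysis section but on no visit list is likely to be missed, and a missed 3-month questionnaire cannot be recovered later.

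For PEQ-S, what is at stake is a summary promised in the primary analysis. It is also the only one of the three mental-status tools that Section 2.2.1 places at follow-up. Its role is unsettled as well: a safety tool in Section 2.2.1, a feasibility measure in Section 8.5, and absent from Section 7.1. For IOS, the durability part of one exploratory endpoint would be lost. For HARSI, reliance on the text lists would leave no value before psilocybin, so the hypothesised change in shame could not be computed.

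**Working it through.** The plan gives no figure to reproduce; the check compares lists.

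**Step 1. Find PEQ-S and IOS in every subject contact in Section 6.4.**

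| Contact | Self-report or rated measures listed | PEQ-S | IOS |
|---|---|---|---|
| Phone screen (6.4.1) | DS-II, ICG | no | no |
| Enrolment (6.4.2) | screening battery | no | no |
| Baseline (6.4.3.1) | 19 self-report scales | no | yes |
| Sessions 1-4 (6.4.4.1) | GQ, C-SSRS, observer ratings | no | no |
| Drug day and day after (6.4.4.2) | CrEQ; MEQ-30, ChEQ, STAI, SAHD, MQoL, C-SSRS | no | no |
| Sessions 5-10 (6.4.4.3) | CTC, GQ, CESD-R, DS-II, ICG, PCL-5, HARSI, C-SSRS, observer ratings | no | no |
| Week 8 (6.4.5.1) | 19 self-report scales | no | yes |
| Week 10 (6.4.6.1) | DS-II, ICG, C-SSRS | no | no |
| 3 months (6.4.6.2) | 20 self-report scales | no | no |
| Interviews (6.4.6.4) | no questionnaires | no | no |

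PEQ-S has 0 scheduled collections. IOS has 2 of its 3 required time points. The two measures summarised alongside PEQ-S in Section 8.5 are both scheduled: CrEQ on the drug day, CSS at Week 8 and 3 months.

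**Step 2. Compare the 3-month packet with what the endpoints need.** Section 2.2.2 requires a 3-month value for 18 measures: DS-II, ICG, AMAS, CESD-R, MQoL, SAHD, STAI, DUFSS-5, PTGI-SF, PCL-5, IPIP-OE-20, MAIA, SCS-R, NR-6, AUDIT, DUDIT, ECR-M16 and IOS. Seventeen are in the packet; IOS is the exception. It is also the only one of the 19 baseline scales, and the only one of the 19 Week 8 scales, that the packet omits. That pattern points to an oversight.

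**Step 3. Compare the packet with baseline.** Of the 20 packet scales, 18 are in the Section 6.4.3.1 list. The exceptions are CSS, a satisfaction score that needs no baseline, and HARSI. All 3 HARSI collections in the text come after psilocybin. The other 4 scales in the session 5 battery (CESD-R, DS-II, ICG, PCL-5) are in both the enrolment and the baseline lists.

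**Step 4. Burden of adding PEQ-S.** Item counts from Section 6.2, for the 19 packet scales that have one:

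AMAS 1 + AUDIT 10 + CESD-R 20 + DS-II 16 + DUDIT 11 + DUFSS-5 5 + ECR-M16 16 + HARSI 22 + ICG 19 + MQoL-RS 4 + NR-6 6 + PCL-5 20 + SAHD 20 + SCS-R 8 + STAI 40 + PTGI-SF 10 + IPIP-OE-20 20 + MAIA-R 12 (5 + 4 + 3) + CSS 4 = 264.

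The CTC is a checklist of 7 categories with no item count. PEQ-S adds 59 + 4 = 63 items. 63/264 = 23.9%; counting the CTC categories, 63/271 = 23.2%.

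**Appendix A.** The table is broken in the text available for review, so missing marks in it prove nothing. It shows no row for PEQ-S or IOS, which agrees with the above, but the finding rests on the Section 6.4 text. It appears to mark HARSI at enrolment and baseline.

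**The case against.** The best counter-argument is that little hangs on either measure. Section 2.2.1 defines safety by the rate of adverse reactions; PEQ-S is a supporting tool with one descriptive median, and no test or stopping rule uses it. IOS is one exploratory process measure among many. This stands, and it limits the weight of the point.

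A second argument is that Section 2 is itself part of the protocol: it places PEQ-S at follow-up and IOS at 3 months, so data are lost only if staff follow Section 6.4 and ignore Section 2. The two sections do conflict, but the visit lists are the operational instructions, and the phrase in Section 2.2.1 does not say which follow-up contact is meant.

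Third, the Abstract's silence on PEQ-S is weak evidence that its role is unsettled. MoCA is also missing from both Abstract lists, and one measure can inform both safety and feasibility. That is fair. The difference between Sections 2.2.1, 7.1 and 8.5 remains and needs one consistent statement.

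Fourth, Appendix A appears to schedule HARSI before treatment, so that loss occurs only if staff use the text lists. This also stands; HARSI is a text-to-table mismatch.

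**Conclusion.** The point holds. As scheduled in Section 6.4, PEQ-S is collected at no visit (0 of 2 follow-up contacts, or 0 of 3 if the interviews are counted), so the median promised in Section 8.5 would have no data. IOS is collected at 2 of 3 required times, so its change to 3 months could not be computed. Both statements assume that staff work from the Section 6.4 lists.

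The consequence is limited. The adverse-reaction rate remains computable, and CORF, CESD-R, STAI and PCL-5 are still collected at 3 months. The IOS and HARSI losses would be exploratory. It should still be corrected because one gap reaches the primary analysis and the remedy is cheap.

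**What to change.** In one amendment:

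- **PEQ-S:** either add it to Section 6.4.6.2 and Appendix A and state its role once, consistently across Sections 2.2.1, 7.1 and 8.5; or delete it from Sections 2.2.1 and 8.5 and also from Section 6.2. Scheduling it adds 63 items to a mailed packet and could lower the return rate. Deleting it adds no burden but gives up the only mental-status tool that Section 2.2.1 places at follow-up.
- **IOS:** add it to the 3-month packet and Appendix A, and describe it in Section 6.2. This is one more measure, already in use at two visits.
- **HARSI:** add it to the lists in Sections 6.4.2 and 6.4.3.1. This is a text edit if Appendix A is already being followed.

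Three smaller items can be tidied at the same time; the conclusion does not depend on them. The PTGI-SF endpoint in Section 2.2.2 should be worded as change from pre-treatment, as Sections 1.4 and 8.5.1 assume. Section 6.4.6.2 should say who carries out the 3-month C-SSRS and adverse-event screen, and how; this may lengthen that contact. QoLLTI-Fv2, described in Section 6.2 but collected at 0 of 3 caregiver visits, should be scheduled, or the Introduction's promise of quantitative caregiver quality of life should be dropped.

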#### 2.2.2 Exploratory Endpoints

Preliminary efficacy will be assessed with the primary clinical outcome measures:

- Change in demoralization will be defined as the difference in pre-treatment, post-treatment, and 3-month follow-up scores of the Demoralization Scale-II.
- Change in complicated grief will be defined by the difference in pre-treatment, post-treatment, and 3-month follow-up mean scores of the Inventory of Complicated Grief.

Preliminary efficacy will also be explored with the following secondary endpoints (See Section 5 for details on individual measures):

- Change in ART medication adherence will be defined as the difference in pre-treatment, post-treatment, and 3-month follow-up mean scores of the ART Medication Adherence Scale.
- Change in depression will be defined by the difference in pre-treatment, post-treatment, and 3-month follow-up mean scores of the Center for Epidemiologic Studies Depression Scale—Revised. Change in subject quality of life will be defined by the difference in pre-treatment, post-treatment, and 3-month follow-up mean scores of the McGill Quality of Life Questionnaire—Revised.
- Change in desire for hastened death will be defined as the difference in pre-treatment, post-treatment, and 3-month follow-up mean scores of Schedule of Attitudes towards Hastened Death.
- Change in anxiety will be defined as the difference in pre-treatment, post-treatment, and 3-month follow-up mean scores of the State-Trait Anxiety Inventory.
- Change in social support will be defined as the difference in pre-treatment, post-treatment, and 3-month follow-up mean scores of the Duke/UNC Functional Social Support Questionnaire-5.
- Post-traumatic growth due to the intervention will be defined by post-treatment and 3-month follow-up mean scores of Post-Traumatic Growth Inventory—Short Form.
- Change in PTSD symptoms will be defined as the difference in pre-treatment, post-treatment, and 3-month follow-up mean scores of the PTSD Checklist-5.
- Change in global clinical status will be defined as the difference in pre-treatment and post-treatment mean scores of the Clinical Global Impressions Scale completed by an clinical rater.
- Change in openness to experience will be defined as the difference in pre-treatment, post-treatment, and 3-month follow-up mean scores of the International Personality Item Pool—Openness to Experience-20 scale.
- Change in mindfulness will be defined as the difference in pre-treatment, post-treatment, and 3-month follow-up mean scores of subscales of the Multidimensional Assessment of Interoceptive Awareness.
- Change in social connectedness will be defined by the difference in pre-treatment, post-treatment, and 3-month follow-up mean scores of the Social Connectedness Scale—Revised.
- Change in Nature Relatedness will be defined by the difference in pre-treatment, post-treatment, and 3-month follow-up mean scores of the Nature Relatedness Scale, Short Form Version.
- Change in alcohol and drug use will be defined by different in the baseline and 3-month follow-up AUDIT and DUDIT scores

Psychotherapeutic process and mechanisms will be explored with the following endpoints:

- Change in group cohesion will be defined as the difference in rate of Group Questionnaire score change pre- and post-psylocybin.
- Change in group process will be assessed as the difference in rate of progression of

---

the Hill Interaction Matrix score pre- and post-psilocybin.

- Change in group process will be assessed as the change in the Individual Group Member Interpersonal Process Scale over time.
- Expectancy effects will be estimated based on the pre-psilocybin total score of the Credibility/Expectancy Questionnaire.
- Subjective experience of a psilocybin treatment session will be evaluated with the Mystical Experience Questionnaire—30 and the Challenging Experience Questionnaire.
- Change in attachment security will be defined as the difference in pre-treatment, post-treatment, and 3-month follow-up mean scores of the Experiences in Close Relationships scale—Modified 16.
- Qualitative analysis of therapy session video footage, semi-structured patient interviews, focus groups and process notes written by study staff.
- Change in inclusion of other in self will be defined by the difference in pre-treatment, post-treatment, and 3-month follow-up results of the Inclusion of Other in Self measure.

## 3 Study Design

### 3.1 Characteristics

This is a Phase I open-label pilot mixed-methods study of the safety and feasibility of an 8-week group psychotherapy intervention that includes one individual drug session with oral synthetic psilocybin. This intervention is designed to treat demoralization in LTAS. Groups of 6 subjects will be run in sequence. Safety data will be gathered before, during, immediately after, and for 3 months after the intervention. Subjects will complete self-report measures and semi-structured interviews related to acceptability and subjective experience. Exploratory analyses will be conducted of clinical outcomes. Exploratory analyses will also include quantitative and qualitative assessments of psychotherapeutic process mechanisms.

